**Changes in tissue and cerebral oxygenation following spinal anesthesia
in neonates, infants, and children**

NCT02840253

IRB Approval Date: 6/14/2016

Title: Changes in tissue and cerebral oxygenation following spinal anesthesia in neonates, infants, and children

Investigators:

1. [name]
2. [name]
3. [name]

Describe the background and rationale for this project. Reference to peer reviewed literature is desirable: Animal studies suggest that anesthesia may increase neuronal apoptosis in the neonatal and developing brain of the very young.¹⁻³ Primate and retrospective cohort studies also indicate the possibility of long-term cognitive deficits as a side effect of anesthesia.⁴⁻⁶ The molecular pathways that could cause neurotoxic effects of anesthesia are currently not known. However, significantly increased apoptosis of neurons after anesthesia has been observed in animal studies with rodents and primates. To reduce the potential risk of neurological damage to the brain from anesthesia, there has been a resurgence in the use of spinal anesthesia instead of general anesthesia for specific surgery procedures involving the GU system, lower abdomen, and extremities.⁷

In line with these concerns, we have started an awake spinal anesthesia program in conjunction with our pediatric surgical colleagues. Patients are offered the option of awake spinal anesthesia instead of general anesthesia for appropriate surgical procedures. Previous studies have demonstrated a lack of significant hemodynamic changes in neonates and infants following spinal anesthesia; however, there are limited data regarding its impact on tissue oxygenation. The goal of the current study is to assess changes in tissue and cerebral oxygenation using non-invasive near infrared spectroscopy following spinal anesthesia.

How will your study be funded (i.e., will you use departmental funds, submit a grant application, etc.): No funding is required.

Provide a potential start date for your study to be included in the IRB application: 1 July 2016

Describe the significance of the proposed research: Although generally safe and effective, this study will demonstrate that tissue and cerebral oxygenation are maintained during spinal anesthesia in the awake in infants. Tissue oxygenation will be assessed non-invasively using near infrared spectroscopy, a device that is commonly used in our operating rooms to assess cerebral and tissue oxygenation.⁸⁻¹⁰

State the primary and secondary objectives of the study:

1. To evaluate changes in tissue and cerebral oxygenation following spinal anesthesia in infants.

If this research is hypothesis driven, succinctly state the hypothesis:

There will be no clinically significant change in tissue and cerebral oxygenation after spinal anesthesia.

Outline the major steps and methodologies in the clinical protocol.

If necessary, include a description of any procedures being performed already for diagnostic or treatment purposes. Clearly differentiate between these procedures. This prospective study will include 50 patients presenting for spinal anesthesia. There will be no change in the anesthetic or perioperative care of these patients. All patients will receive spinal anesthesia per our routine clinical guidelines that have been established. Tissue and cerebral oxygenation will be monitored using near infrared spectroscopy (NIRS). The device is applied non-invasively like pulse oximetry to a muscle bed (thigh or upper arm) and the forehead to measure tissue oxygenation. These devices are used routinely in the operating room and the cardiothoracic intensive care unit. These devices are routinely used in various high risk clinical scenarios. The use of NIRS during these cases is the only modification from standard clinical practice that will occur for the purpose of the study. NIRS will be recorded every 30 seconds for 2 minutes prior to spinal anesthesia and these values averaged as the baseline. Following that NIRS will be recorded every 1 minute for 30 minutes. The following data will also be recorded: BP, HR, and oxygen saturation.

Identify the variables to be measured and how they will be statistically evaluated: Changes in tissue and cerebral oxygenation before and the following the administration of blood will be evaluated using a paired t-test. To determine if there are differences between autologous and allogeneic blood, a non-paired t-test will be used.

References:

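### Does the mismatch between a title covering neonates, infants and children and an objective naming only infants require a change to the plan?

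*Combined protocol and SAP*

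**What the plan says.** The age group is named differently from place to place in the protocol.

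- Title: "Title: Changes in tissue and cerebral oxygenation following spinal anesthesia in neonates, infants, and children".
- Background: earlier evidence is cited for two groups, "Previous studies have demonstrated a lack of significant hemodynamic changes in neonates and infants following spinal anesthesia". The aim given in the same section, "The goal of the current study is to assess changes in tissue and cerebral oxygenation", names no age group.
- Significance: "this study will demonstrate that tissue and cerebral oxygenation are maintained during spinal anesthesia in the awake in infants".
- Objectives (only one is listed): "To evaluate changes in tissue and cerebral oxygenation following spinal anesthesia in infants".
- Hypothesis: "There will be no clinically significant change in tissue and cerebral oxygenation after spinal anesthesia", with no age group.
- Clinical protocol: "This prospective study will include 50 patients presenting for spinal anesthesia". No lower or upper age is given. The same section adds "All patients will receive spinal anesthesia per our routine clinical guidelines that have been established"; those guidelines are not reproduced.

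The extra data listed for recording are blood pressure, heart rate and oxygen saturation; age is not mentioned. The statistical paragraph has no age term, and its tests are worded for blood administration rather than spinal anesthesia.

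**The concern.** The title and the background both list neonates apart from infants, and the title adds children. On that usage the objective leaves out two of the three groups in the title, while the enrolment sentence excludes nobody by age. Even if neonates count as infants, children remain in the title and outside the objective.

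If the 50 patients span several ages and one before/after mean is reported, that mean is not the change in infants that the objective asks for. The hoped-for result is no clinically significant change, so dilution of a real fall in infants by stable older patients would favour it. A claim that oxygenation is maintained in infants could then rest partly on patients who are not infants.

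**Working it through.** **The plan's own figure.** The only design number is 50 patients. The documents give no SD, effect, margin, power or age mix, so 50 cannot be reproduced, and the number of infants among the 50 could be anything from 0 to 50.

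**Size of the discrepancy.** Let f be the share of non-infants, m_I and m_O the mean changes in infants and others, and d = m_O − m_I. Then

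pooled mean = (1 − f)·m_I + f·m_O = m_I + f·d.

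The discrepancy is f·d. It is zero if f = 0 or d = 0, and its sign is the sign of d. With a 6-point fall in infants and f = 30%:

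- others fall 0: 0.7 × 6 + 0.3 × 0 = 4.2, an understatement;
- others fall 3: 0.7 × 6 + 0.3 × 3 = 5.1, a smaller understatement;
- others fall 9: 0.7 × 6 + 0.3 × 9 = 6.9, an overstatement.

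Nothing in the documents favours one of these over another.

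**Would an infants-only analysis detect a fall better?** Assumed inputs: 6-point fall in infants, n = 50, two-sided 5% paired t-test, a common SD of the change within age groups. Pooled SD = √(SD² + f(1 − f)d²). The miss probability comes from the noncentral t distribution with n − 1 degrees of freedom and noncentrality mean × √n / SD. The infants-only test uses 50(1 − f) patients.

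Chance of missing the fall, at SD 10 / SD 12:

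| f | Pooled, others fall 0 | Pooled, others fall 3 | Infants alone |
|---|---|---|---|
| 10% | 4.2 / 13.0% | 2.4 / 9.3% | 2.4 / 9.3% |
| 20% | 10.1 / 22.4% | 4.0 / 12.6% | 4.1 / 13.1% |
| 30% | 19.9 / 34.3% | 6.2 / 16.7% | 6.8 / 18.0% |
| 40% | 33.2 / 47.6% | 9.2 / 21.4% | 11.2 / 24.6% |

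Worked entry, f = 30%, SD 12, others fall 3: mean 5.1; SD = √(144 + 0.21 × 9) = 12.08; noncentrality = 5.1 × √50 / 12.08 = 2.99; miss probability 16.7%. For 35 infants alone: 6 × √35 / 12 = 2.96 on 34 degrees of freedom; miss probability 18.0%.

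The advantage of restricting to infants therefore depends on the others showing little or no fall. If they fall by half as much, the two analyses tie at f = 10%, and the infants-only test misses more often from 20% upward. At SD 5 the pooled test misses at most 1% of the time even when the others do not fall, so there the choice hardly matters.

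**Cost of restricting.** The 95% half-width is t(0.975, n − 1) × SD / √n. With 45, 40, 35 or 30 patients in place of 50 it grows by about 6, 13, 21 or 31%. At SD 8 it goes from 2.27 (n = 50) to 2.75 (n = 35).

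**The case for a change.** The best case for a change is that the inconsistency is plain on the page and cheap to mend. The document's own usage separates the three age groups, no age limit is stated, and nothing in the analysis text would separate an infant result from a mixed one. Without recorded ages a reader could not tell whom the result describes. Even in the kindest reading the title misdescribes the study.

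The textual part of this stands: the wording does differ. The inferred harm is weaker. It needs non-infants to be enrolled and also to respond differently, and the documents show neither. The cited evidence concerns neonates and infants, the sentence in the significance section is itself loosely written, and the routine guidelines may limit age in practice, though that cannot be checked. The list of extra data need not be complete; a patient's age is ordinarily in the anesthetic record. The lack of an age term carries little weight while the stated tests refer to a different exposure altogether, which is a separate matter.

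**Conclusion.** The concern is right about the wording but does not support a change to the plan. The title is broader than the objective and the significance statement, and no age range is given. If only infants are enrolled, the consequence is confined to the title. If other ages are enrolled, the pooled estimate differs from the infant mean by f × d, in an unknown direction and by an amount the documents do not allow anyone to size. A claim that a fall in infants would be understated does not follow.

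The gap is one that those reporting the study would fill in the ordinary way: give the ages enrolled, say whether neonates are counted as infants, and word the conclusion for those ages. Beyond that, choosing between an infants-only primary set and a wider objective is a trade-off. Restriction gives the estimate the objective names, at the price of intervals about 6 to 31% wider with 45 down to 30 infants, and it lowers the miss rate only if the others fall much less than infants. These figures rest on an assumed 6-point fall and assumed SDs; none comes from the documents.

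### The hypothesis is that oxygenation does not change importantly, but the only before/after analysis is a paired t-test of zero change, with no margin and worded for blood administration

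*Combined protocol and SAP*

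**What the plan says.** The hypothesis section states: "There will be no clinically significant change in tissue and cerebral oxygenation after spinal anesthesia". The section on the significance of the research goes further: "this study will demonstrate that tissue and cerebral oxygenation are maintained during spinal anesthesia in the awake in infants". The single listed objective is milder and asks only for changes to be evaluated.

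The methods section gives the design: "This prospective study will include 50 patients presenting for spinal anesthesia". Baseline is the average of near infrared spectroscopy (NIRS) readings taken over the 2 minutes before the spinal. For the period afterwards, "Following that NIRS will be recorded every 1 minute for 30 minutes".

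The statistical section consists of two sentences. The first reads: "Changes in tissue and cerebral oxygenation before and the following the administration of blood will be evaluated using a paired t-test". The second plans an unpaired t-test that compares patients by the source of the blood they were given, their own or a donor's.

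Neither mentions spinal anesthesia. The protocol contains no number for a clinically significant change, no equivalence or confidence-interval criterion, no alpha, no SD and no power calculation.

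**The concern.** The hypothesis says that any change is too small to matter. A paired t-test with no stated margin asks whether the mean change is exactly zero, which is a different question. Failing to reject zero does not show that the change is small, because imprecise data give the same result. Rejecting zero does not show that the change is large enough to matter, because precise data can detect a trivial shift.

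Taken literally, the plan is in a worse position. Its before/after test concerns blood administration, which is not part of the described procedures, so no test of change after spinal anesthesia is specified. The second test compares two types of blood and has no bearing on the hypothesis. Even if blood is read as a slip for spinal anesthesia, the test lacks an input: the 30 post-spinal readings are not reduced to a value that can be paired with baseline.

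At stake is the study's main conclusion. The protocol already expects to find oxygenation maintained, so a non-significant result could be reported as confirming it when the data are only noisy. A significant result could be reported as contradicting it when the change is unimportant.

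**Working it through.** **Inputs from the protocol.** n = 50 patients in one group, analysed by paired t-test (df = 49). The sample size cannot be reproduced, because no alpha, power, SD or effect size accompanies it.

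**Assumptions (none is in the protocol).** Two-sided 5% for the t-test; SD of the paired change 5, 8, 12 or 15 saturation points; an illustrative margin of 5 points; all 50 patients analysed.

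**1. Precision.** The 95% half-width is t(0.975, 49)/√50 × SD = 2.010/7.071 × SD = 0.284 SD. The 90% half-width is 1.677/7.071 × SD = 0.237 SD.

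**2. Two hypothetical results.**
- Mean change 2, SD 5: SE = 5/7.071 = 0.707, t = 2.83, p = 0.007, 95% CI 0.6 to 3.4. This is significant, yet the whole interval is below 5 points.
- Mean change 5, SD 20: SE = 20/7.071 = 2.83, t = 1.77, p = 0.083, 95% CI −0.7 to 10.7. This is non-significant, yet the interval reaches beyond 10 points.

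The p-values point the opposite way from the intervals. Without a margin, neither result can be classed as supporting or refuting the hypothesis.

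**3. How often the t-test misses a true 5-point change.** Noncentral t with noncentrality 5√50/SD:

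| SD of change | Noncentrality | P(non-significant) |
|---|---|---|
| 5 | 7.07 | <0.1% |
| 8 | 4.42 | 0.9% |
| 12 | 2.95 | 18% |
| 15 | 2.36 | 36% |

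The miss rate passes 5% once the SD exceeds about 9.6.

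**4. How often the t-test flags a small change.** For a true 2-point change with SD 5, the noncentrality is 2 × 7.071/5 = 2.83 and power is 79%. In the same setting the 90% CI lies inside ±5 points 99% of the time.

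**5. Power of a rule that addresses the hypothesis.** The rule is that the 90% CI lies within ±5 points (two one-sided tests at 5% each), computed by integrating over the sample SD. The both-measurements column requires cerebral and tissue to pass, assuming independence and equal SDs, so it is the square of the unrounded single-measurement figure.

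| SD | One measurement, true change 0 / 2 | Both measurements, true change 0 / 2 |
|---|---|---|
| 5 | >99% / 99% | >99% / 99% |
| 8 | 99% / 83% | 99% / 70% |
| 12 | 79% / 53% | 63% / 28% |
| 15 | 50% / 35% | 25% / 12% |

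Positive correlation between the two measurements softens the joint requirement. At SD 12, simulation with 100,000 replicates gives about 65% and 36% at correlation 0.5, and about 70% and 42% at 0.8. When the true change equals the margin, the single-measurement rule passes wrongly about 5% of the time. That error rate is controlled whatever the SD, which is not so for the miss rates in step 3.

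**6. Is 50 enough?** In SD units, with a true change of zero, 50 patients give 80% power for a margin of about 0.42 SD. By the normal approximation n = ((1.645 + 1.282)/margin)², margins of 0.3, 0.4 and 0.5 SD need about 96, 54 and 35 patients. The answer therefore turns on a margin and an SD that the protocol does not supply.

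**The case against.** The strongest reply is that the harm is conjectural. The protocol never says that p > 0.05 will be read as maintained oxygenation. The expectation that this will be demonstrated sits in a section on significance, not in a decision rule, and the stated goal and objective are only to assess or evaluate changes. An estimate with its interval would meet that objective, and the planned data would yield one. The size of the problem is also unknown: at SD 5 or 8 a true 5-point change would almost never be missed, and nothing in the protocol favours the larger SDs. Finally, the blood wording looks like carried-over text, care is unchanged, and no treatment decision in the study depends on the p-value.

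Much of this is fair. The error rates are conditional, and the objective taken alone could be met. But the plan does not promise an interval, and an interval without a margin still could not decide the hypothesis. A small SD removes one risk and creates the other, since a trivial change then becomes significant. Carried-over wording or not, the sole hypothesis has no analysis that can establish it.

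The reply is also right that the plan does not demand a joint conclusion for cerebral and tissue oxygenation. Separate conclusions are possible if that is stated beforehand.

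**Conclusion.** The concern holds and must be fixed. As written, the plan either tests the wrong exposure or, read charitably, tests zero mean change; neither can establish "no clinically significant change". This conclusion is logical and needs no assumed numbers.

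Its practical size does depend on assumptions. With 50 patients, two-sided 5% and a 5-point margin, the chance of missing a true 5-point change runs from under 0.1% to 36% as the SD of change goes from 5 to 15. At the low end of that range, a 2-point change would be significant about four times in five. Because the plan gives neither the SD nor the margin, the documents cannot place the study within this range.

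**What to change.** - Rewrite the statistical section so that the before/after analysis refers to spinal anesthesia, and remove the comparison of blood types.
- Before analysis, name the post-spinal summary to be compared with baseline for each of cerebral and tissue oxygenation. The mean of the 30 one-minute readings is one option, but it can average away a short fall, so the choice should match what the investigators mean by maintained.
- Before analysis, have the investigators state and justify, for each measurement, the change they regard as clinically significant.
- Report the mean paired change with its confidence interval. Conclude that oxygenation is maintained only if the 90% CI lies within the margin for both measurements. If only falls matter, require the one-sided 95% limit to exclude the margin for both. If separate conclusions are wanted instead, say so in advance.
- Reword the significance section so that the study will assess whether oxygenation is maintained, rather than demonstrate that it is.

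**Cost.** This takes protocol wording, a named summary and an agreed margin, with the same 50 patients and readings. The drawback is a harder claim if variability is high. With the illustrative 5-point margin and SD 12, power for one measurement is 79% (true change 0) or 53% (true change 2). Requiring both lowers this to about 63% or 28% under independence, and by less with positive correlation. The one-sided rule for falls gives 90% or 54% for one measurement at SD 12, for a true fall of 0 or 2 points.

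### The plan does not say which of the 30 post-spinal NIRS readings per site enters the paired t-test, and a non-significant t-test cannot show that there was no clinically significant change

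*Combined protocol and SAP*

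**What the plan says.** All references are to the combined protocol and SAP.

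- **Baseline** (methods section, *Outline the major steps and methodologies*): "NIRS will be recorded every 30 seconds for 2 minutes prior to spinal anesthesia and these values averaged as the baseline". This side of the comparison is fully reduced to one value.
- **Post-spinal readings** (same section): "Following that NIRS will be recorded every 1 minute for 30 minutes". No time point, window, mean, minimum or model follows.
- **Sites** (same section): the sensor is applied "to a muscle bed (thigh or upper arm) and the forehead to measure tissue oxygenation".
- **Sample size** (same section): "This prospective study will include 50 patients presenting for spinal anesthesia". No alpha, SD, effect size or margin accompanies it.
- **Hypothesis**: "There will be no clinically significant change in tissue and cerebral oxygenation after spinal anesthesia". No number is attached to clinically significant.
- **Analysis** (*Identify the variables to be measured*): "Changes in tissue and cerebral oxygenation before and the following the administration of blood will be evaluated using a paired t-test". The reference to blood is a separate defect. Here the sentence is read as before versus after spinal anesthesia.
- **Significance paragraph**: "this study will demonstrate that tissue and cerebral oxygenation are maintained during spinal anesthesia".

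**The concern.** A paired t-test needs one value per patient on each side. The plan defines the first and leaves the second open among about 30 readings at each of two sites. Reasonable analysts could test each minute, average all 30 minutes, average an early window or take the lowest reading. These choices have very different error rates and can disagree on the same data.

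The aim of the study is reassurance, so the direction of the test also matters. A paired t-test looks for a difference. Failing to find one is not evidence that any change is too small to matter, and without a margin there is nothing to judge the estimate against. At stake is whether the published conclusion reflects the data or a choice made after seeing them.

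**Working it through.** **Inputs from the plan.** n = 50; baseline is a mean of readings every 30 seconds over 2 minutes (4 or 5 readings, depending on whether time 0 counts); 30 post-spinal readings; 2 sites. The 50 cannot be reproduced, because none of its inputs is stated.

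**Assumptions (not in the plan).** Two-sided 0.05 per test; complete data; AR(1) correlation ρ between readings one minute apart; independent sites; 5 baseline readings. Depths are in within-patient SDs of one reading. Five models of how the baseline relates to the later readings are used to show the range.

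**1. Testing every minute, no true change.** If all tests were independent: 1 − 0.95^30 = 0.785 for one site and 1 − 0.95^60 = 0.954 for two. The readings are correlated, so this was simulated (4,000 replicates). For each minute, t = mean(reading − baseline) / (SD of that difference / √50), and |t| > 2.01 counts as a change. Share of trials with at least one false change over two sites:

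| Baseline model | ρ = 0.5 | ρ = 0.8 | ρ = 0.95 |
|---|---|---|---|
| Continuous with the later series | 81% | 67% | 53% |
| Independent, uncorrelated readings | 90% | 76% | 45% |
| Independent AR(1) stretch | 79% | 60% | 36% |
| Same series, 10 minutes earlier | 79% | 63% | 43% |
| As row 1, plus a patient-level shift (mean 0, SD 1) | 61% | 51% | 36% |

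The first two rows give the 45% to 90% range; all five extend it down to 36%. For one site alone (continuous series, 4-reading baseline) the rates are 56%, 41% and 32%. One 30-minute mean per patient gives 4.4% to 5.8% per site.

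**2. Two reasonable summaries.** Let every patient fall by 1 SD at minutes 8 to 12.

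- The 30-minute mean moves by 5/30 = 0.167 SD.
- The first-10-minute mean contains minutes 8, 9 and 10, so it moves by 3/10 = 0.30 SD.

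Over the five models and ρ = 0.5 to 0.95, the two t-tests give opposite verdicts in 20% to 66% of trials. With no true change they disagree in 2% to 6%.

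**3. Dilution in the 30-minute mean.** For a k-minute, 1-SD fall the noncentrality is (k/30) × √50 / SD of the mean change. That SD ranges from 0.54 to 1.37 over the models.

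- k = 5: 0.167 × 7.07 / 0.54 = 2.18, and 0.167 × 7.07 / 1.37 = 0.86. The test is non-significant in about 43% and 87% of trials.
- k = 10: 0.333 × 7.07 / 0.54 = 4.36, and 0.333 × 7.07 / 1.37 = 1.72. It is non-significant in about 1% and 61%.

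**4. What non-significance shows.** The 95% interval for a mean change has half-width 2.01/√50 = 0.284 SD of the change. Power is 80% for a true mean change of 0.40 SD and 90% for 0.47 SD. A true change of 0.40 SD would therefore be non-significant in about one trial in five, and the plan has no margin that says whether such a change matters.

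**5. Can 50 patients meet a margin?** With true change 0, the chance that the 95% interval lies inside ±m (m in SDs of the change) is about 2Φ((m − 0.284) × √50) − 1. Squaring gives both sites, if independent.

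- m = 0.4: 0.116 × 7.07 = 0.82, so 59% per site and 34% for both.
- m = 0.5: 0.216 × 7.07 = 1.53, so 87% and 76%.
- m = 0.6: 0.316 × 7.07 = 2.23, so 97% and 95%.

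**6. Lowest reading.** With no true change, each patient's lowest single reading averages 1.9, 1.6 and 1.1 SD below baseline at ρ = 0.5, 0.8 and 0.95. A minimum cannot be tested against an averaged baseline as if it were unselected.

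**The case against.** The strongest reply is that this is a short, unfunded observational study of 50 patients, that a paired t-test is named, and that one sentence naming a summary would close the gap. Much of this stands. A paired t-test on one fixed summary per patient is valid, and serial correlation then needs no separate handling. The reply does not rescue the inference from non-significance, which would remain whichever summary were chosen.

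Four stronger readings are tempting, and the documents do not support them.

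- **That the plan has no test.** It has one. What is missing is the post-spinal value and a basis for concluding no change.
- **That the two-site rule is absent and alpha must be split.** The hypothesis and the significance paragraph both join tissue and cerebral oxygenation with *and*, so both sites must satisfy the claim. No alpha split is then needed.
- **That a 30-minute mean almost always passes a margin despite a real fall, while a simultaneous band almost never does.** With a 1-SD fall and a 1-SD margin, simulation gives 98% to 100% against at most 0.2%. That contrast is built in: the fall equals the margin and occurs in the same five minutes in every patient. Nothing in the documents says that 1 SD is clinically important.
- **That a band would settle the whole-period claim.** When onset varies over 26 minutes between patients, the band lay inside the 1-SD margin at both sites in 20% to 85% of trials in one set of runs, and in 1% to 89% over all five baseline models. It can miss the fall too.

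**Conclusion.** The point holds. The post-spinal side of the only before/after comparison is undefined, and the named test cannot establish the stated hypothesis by being non-significant. This rests on the text and needs no simulation.

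The size rests on assumptions. The ranges of 45% to 90% (false change) and 20% to 65% (opposite verdicts) depend on AR(1) correlation of 0.5 to 0.95, complete data and the baseline models; the first also on independent sites, the second on a fall at the same minutes in every patient. Weaker baseline models bring the first range down to 36%, and correlated sites would lower it further. The figures show that the choice can decide the result. They do not predict what this trial will find.

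The change should be made before the data are seen. The data remain usable and no measurement is lost.

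**What to change.** 1. For each site, name in advance one per-patient summary of change from the averaged baseline, for example the mean over minutes 1 to 30. Report its mean with a 95% confidence interval; a paired t-test on that summary is adequate as a test of difference.
2. Conclude no clinically significant change only if the interval lies inside a margin that the investigators set before seeing the data, at both sites. Do not use non-significance for this.
3. Because a 30-minute mean dilutes a short fall, limit its conclusion to the average over the period.
4. Report as supportive the minute-by-minute mean change with a simultaneous 95% band. Report descriptively each patient's lowest 5-minute mean and the number of patients beyond the margin, noting that a minimum lies below baseline by selection.
5. Do not rest a statement that oxygenation was maintained throughout on the band alone, since it can miss falls whose timing varies between patients.

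**Cost.** Some protocol wording and a slightly longer analysis of readings already scheduled. The band is about 1.3 to 1.6 times as wide as per-minute intervals. A small margin may be out of reach with 50 patients: at 0.4 SD of the change, both sites would pass in only about a third of trials even with no true change.

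### The only statistical text analyses blood administration and autologous versus allogeneic groups, neither of which exists in this single-cohort spinal anesthesia study

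*Combined protocol and SAP*

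**What the plan says.** The statistical plan is in the protocol section *Identify the variables to be measured and how they will be statistically evaluated*, and it has two sentences:

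- The first sets out a test within patients: "Changes in tissue and cerebral oxygenation before and the following the administration of blood will be evaluated using a paired t-test".
- The second sentence adds a comparison of two blood types: "To determine if there are differences between autologous and allogeneic blood, a non-paired t-test will be used".

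The other sections describe a different study:

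- The single objective is "To evaluate changes in tissue and cerebral oxygenation following spinal anesthesia in infants". The hypothesis and the goal in the background section also name spinal anesthesia as the exposure.
- On the sample, the methods section (*Outline the major steps and methodologies*) says: "This prospective study will include 50 patients presenting for spinal anesthesia". All of them receive the same anesthetic technique under routine guidelines.
- On procedures: "The use of NIRS during these cases is the only modification from standard clinical practice that will occur for the purpose of the study".
- On measurement: "NIRS will be recorded every 30 seconds for 2 minutes prior to spinal anesthesia and these values averaged as the baseline". Then: "Following that NIRS will be recorded every 1 minute for 30 minutes". The sensors sit on the forehead and on a muscle bed.
- On other data: "The following data will also be recorded: BP, HR, and oxygen saturation".

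**The concern.** The exposure and the groups in the statistical section do not belong to this design. The wording looks carried over from a protocol about transfusion, although the document does not say where it came from.

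The two sentences fail to different degrees. The unpaired test needs two groups and a variable recording blood type, and the study has neither. The paired test names the right outcome and has the right before-and-after form, but it is tied to an event that is not part of the study.

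This is the only analysis text in the protocol. If it does not apply, the study enters analysis with no prespecified method for its one objective. Correcting the exposure would still leave open which post-spinal value is compared with baseline. A fixed minute, the last reading, the lowest reading and the 30-minute mean estimate different quantities and can give different answers. The choice matters here because the significance section already states, as the expected result, that oxygenation is maintained.

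**Working it through.** The defect is a mismatch of text, so the main check sets the statistical section beside the design.

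| Element | Design sections | Statistical section |
|---|---|---|
| Exposure | Spinal anesthesia | Administration of blood |
| Groups | One cohort of 50, all treated alike | Autologous and allogeneic blood |
| Outcome | Tissue and cerebral oxygenation | Tissue and cerebral oxygenation |
| Contrast | Before and after, within patient | Before and after, within patient (first sentence); between groups (second sentence) |
| Grouping variable recorded | None: the list is NIRS, BP, HR and oxygen saturation | Blood type required |

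The exposure and the groups disagree. The outcome and the within-patient contrast agree, so the first sentence is recoverable and the second is not. Blood administration and the two blood types appear nowhere else in the document. The nearest mention is the title of a cited reference on isovolemic hemodilution, which is not part of the design. Both statistical sentences are complete and legible, so neither redaction nor text extraction explains the mismatch.

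**What remains after the exposure is corrected.** Inputs are from the methods section.

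- Baseline: the 30-second readings over 2 minutes are averaged to 1 value per site.
- Post-spinal: one reading per minute × 30 minutes = 30 readings per site (31 if minute 0 is counted).
- Two sites: 30 × 2 = 60 readings per patient. Over 50 patients: 60 × 50 = 3,000.

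A paired t-test takes one before value and one after value per patient. The before value is defined. The after value is not: there are 30 candidate readings per site, plus any summary of them.

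**What the completed test would deliver.** Assume one named summary per site and all 50 patients contributing.

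- Degrees of freedom: 50 − 1 = 49.
- Critical value: t(0.975, 49) = 2.010.
- 95% confidence interval half-width: 2.010 / √50 = 2.010 / 7.071 = 0.284 × SD of the within-patient change.

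The protocol gives no SD, so the half-width can be stated only in SD units. It also gives no significance level, power or effect size, so there is no planned calculation to reproduce for the 50 patients. The 95% level is the conventional one, used here as an assumption.

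**The case against.** The strongest reply is that this is an obvious slip. The first sentence already names the objective's outcome, a before-and-after contrast and a test, and the methods section defines a pre-spinal baseline followed by a series of readings. Any reader would substitute spinal anesthesia for blood. On that view it overstates the case to say that no applicable analysis is given, and the undefined post-spinal summary is a separate gap that correct wording would also have left.

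Part of this stands. The paired form does fit the design and the substitution is easy. But it is an inference by the reader, and the protocol does not commit the investigators to it. The open summary is a distinct gap, yet it shows why changing one word would not produce a test that can be run.

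Three further cautions are fair:

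- The 60 readings per patient are not 60 alternative answers, because both sites are outcomes in the objective. The relevant count is 30 per site, and summaries such as the mean or minimum add to it.
- The 0.284 SD half-width describes precision after the correction. It does not measure the defect.
- A 30-minute mean can hide a short fall in oxygenation. The start of the 30 minutes is also not precisely defined, and the muscle sensor may be on the thigh or the upper arm. Any replacement sentence should settle these points.

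None of these removes the mismatch.

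**Conclusion.** The concern holds, and the section must be corrected before data are analysed. Both statistical sentences name an exposure or grouping outside the design. The unpaired test cannot be carried out with the data to be recorded. The paired test is recoverable, but even with the right exposure it lacks a defined post-spinal value, with 30 candidate readings per site against one averaged baseline.

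This conclusion rests on the text alone and on no assumed figure. Only the precision statement (49 degrees of freedom, half-width 0.28 SD) depends on all 50 patients contributing and on one summary per site. The margin for a clinically significant change, multiplicity and the basis for 50 patients are separate questions. Without a margin, the corrected analysis estimates the change the objective asks about but cannot by itself decide the hypothesis.

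**What to change.** Delete the autologous versus allogeneic comparison. Replace the first sentence with wording such as:

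> For each sensor site (forehead and muscle), the within-patient change from the averaged 2-minute pre-spinal baseline to the mean of the 1-minute readings over the 30 minutes after spinal anesthesia will be evaluated with a paired t-test and reported with a 95% confidence interval.

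The 30-minute mean is a default. If the investigators care more about a transient fall or a particular minute, they should name that one summary instead, before the data are examined. The same paragraph should say when the 30 minutes start and whether thigh and upper-arm readings are treated as one muscle site.

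The cost is a one-paragraph amendment. It is meant to use the readings already scheduled and needs no extra patients, data or procedures.
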